# 5.4.5.6. Dose Reductions, Interruptions and Discontinuation Criteria

# 5.4.5.6.1. Part A Monotherapy

Following dose interruption, cycle delay due to toxicity, or observation of late immune related DLTs such that the current dose of treatment is now considered to be above the MTD (see Section 3.2.1 Late Immune Related DLTs), the PF-04518600 dose may need to be reduced when treatment is resumed.

No specific dose adjustments are recommended for Grade 1/2 treatment-related toxicity. However, investigators should always manage their patients according to their medical judgment based on the particular clinical circumstances.

Dose reduction of PF-04518600 by 1 and, if needed, 2 dose levels will be allowed depending on the type and severity of toxicity observed. Patients enrolled in the first (0.01 mg/kg) cohort should be discontinued from the study if dose reduction is required. Patients requiring more than 2 (or 1 for the first cohort) dose reductions will be discontinued from the treatment and entered into the follow-up phase, unless otherwise agreed between the investigator and the sponsor. For example, if a patient has clear signs of clinical benefit, and if the investigator considered it to be in the best interest of the patient, they may be allowed to stay on study at a further reduced dose after recovery and appropriate dose interruption. All dose modifications/adjustments must be clearly documented in the patient's source notes and CRF.

Once a dose has been reduced for a given patient, all subsequent cycles should be administered at that dose level, unless further dose reduction is required. Dose re-escalation is not allowed

Patients experiencing a DLT may resume dosing at the next lower dose level once adequate recovery is achieved. No dose reductions are planned for patients experiencing toxicities other than those listed as DLTs. However, patients experiencing recurrent and intolerable Grade 2 toxicity may resume dosing at the next lower dose level once recovery to  $\leq$  Grade 1 or baseline is achieved.

Recommended dose reductions are illustrated in Table 5.

Table 5. Dose Modification for Drug Related Toxicity at Start of Subsequent Cycle in Part A

Event	Action
Grade 3 or 4 non-hematologic toxicity considered related to PF-04518600 per investigator judgment (including persistent nausea, vomiting, diarrhea despite optimal medical therapy), excluding clinically manageable electrolyte abnormalities.	
 
Hold PF-04518600 infusion until recovery to Grade 0-1 or baseline and reduce by 1 dose level.
 
If toxicity (Grade 3-4) reoccurs despite reduction, patient may be dose reduced again by 1 more dose level upon recovery to Grade 0-1 or baseline.
 
Prompt palliative and supportive measures mandated per local standard of care (eg, antiemetic).
 
Patients who experience Grade 4 non hematologic toxicities despite intervention should be discontinued from the study, unless restarting treatment at reduced dose level is in the patient's best interest per investigator judgment and after consultation with Pfizer's medical monitor (eg, clear clinical benefit and no alternative treatment options).
 

Hematologic toxicity considered related to PF-04518600 per investigator judgment  • Grade 4 neutropenia, ie, ANC <500 mm³ (1.0 x 10  /L) for more than 7 days; or,  • Febrile neutropenia, ie, fever >38.3°C or a sustained temperature of ≥38°C (100.4°F) with ANC <1000/mm³; or,  • Grade 4 Thrombocytopenia, ie, PLTS <25,000 mm³ (25.0 x 10  /L); or,  • Grade 3 Thrombocytopenia, ie, PLTS <50,000 mm³ (50.0 x 10  /L) with bleeding.	
 
Hold PF-04518600 until recovery of ANC to         ≥1.0 x 10^9/L (1,000 cells/mm³) and platelets         ≥75 x 10^9/L (75,000 cells/mm³). For HCC         patients, a lower threshold for platelets can be         considered after discussion with the sponsor's         medical monitor (eg, 40,000 cells/mm³),         depending on the shift from baseline.
 
Reduce PF-04518600 by 1 dose level.
 
If toxicity reoccurs (grades a described on the left         side) despite dose reduction, patient may either be         held until recovery and continuation at same dose,         or undergo further dose reduction by 1 more dose         level.
 

Other grade 4 hematologic toxicity considered related to PF-04518600 per investigator judgment.	
 
Hold PF-04518600 until recovery to Grade 0-1 or baseline and reduce PF-04518600 dose by 1 dose level.
 
If toxicity reoccurs (Grade 4) despite dose reduction, patient may either be held until recovery and continuation at same dose, or undergo further dose reduction by 1 more dose level.
 

No recovery of toxicities within 4 weeks of scheduled PF-04518600 infusion.	Discontinue treatment, unless restarting treatment at reduced dose level (either lowest dose level tested or more than 2 dose level reduced) is in the patient's best interest per investigator judgment and after consultation with Pfizer's medical monitor (eg, clear clinical benefit and no alternative treatment options).

Please refer to Section 9.6.3 for (12-Lead) Electrocardiogram (ECG) events that may lead to dose reductions or discontinuations.

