# 4.1.1. Part A Monotherapy

- 1. Part A1 only: Patients with histological or cytological diagnosis of HNSCC, HCC, melanoma, or clear cell RCC who progressed on or are intolerant to standard therapy, for which no standard therapy is available or who decline standard therapy.
- 2. Part A2 only: Patients with histological or cytological diagnosis of advanced/metastatic HCC who are treatment naïve and have declined standard of care, or have had at least 1 prior line of systemic therapy. Prior anti-PD-L1/PD-1 therapy is allowed.
- 3. Patients must have at least one measurable lesion as defined by RECIST version 1.1, be willing to undergo the mandatory biopsies and there is no excessive risk from biopsy as judged by the Investigator.
- 4. Adults (men and women) age  $\geq 18$  years (for Japan only:  $\geq 20$  years of age).
- 5. Eastern Cooperative Oncology Group (ECOG) Performance Status (PS) 0 or 1.
- 6. Adequate Bone Marrow Function, including:
  - ANC  $\ge 1,500/\text{mm}^3 \text{ or } \ge 1.5 \times 10^9/\text{L}.$
  - ANC for HCC only  $\ge 1,000/\text{mm}^3$  or  $1.0 \times 10^9/\text{L}$ .
  - Platelets  $\ge 100,000/\text{mm}^3$  or  $\ge 100 \times 10^9/\text{L}$ .

- Platelets for HCC only: ≥60,000/mm^3.
- Hemoglobin ≥9 g/dL. Limited transfusions to reach this value are allowed, after discussion with sponsor's medical monitor. There should not be a chronic need for transfusions in the recent (approximately 3 month) past.
- 7. Adequate Renal Function, including:
  - Serum creatinine ≤1.5 x upper limit of normal (ULN) or estimated creatinine clearance ≥60 ml/min as calculated using the method standard for the institution. If an estimated creatinine clearance is believed to be inaccurate for a patient, 24 hr urine collection with actual assessment of creatinine clearance is allowed.
- 8. Adequate Liver Function (all patients, except HCC, see Inclusion Criteria 9), including:
  - Total serum bilirubin  $\leq 1.5$  x ULN unless the patient has documented Gilbert syndrome.
  - Aspartate and alanine aminotransferase (AST & ALT)  $\leq$  2.5 x ULN;  $\leq$  5.0 x ULN if there is liver involvement secondary to tumor.
- 9. Inclusion for HCC patients only:
  - Child-Pugh Class A or B with a score of 7 (see Appendix 3) and no prior history of hepatic encephalopathy.
  - Serum bilirubin ≤3 mg/dL.
  - Serum Albumin ≥2.8 g/dL.
  - AST and ALT  $\leq$  5.0 x ULN.

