### **5.4.5.5. Dose Delay**

Re-treatment following treatment interruption for treatment related toxicity or at the start of any new cycle may not occur until all of the following parameters have been met:

- ANC  $\ge 1,000/\text{mm}^3$ .
- Platelets count ≥50,000/mm³. HCC only: based on investigator judgment, after consultation with sponsor's medical monitor, change from baseline will be considered, and levels of ≥25,000/mm³ may be acceptable.
- Non-hematologic toxicities have returned to baseline or Grade ≤1 severity (or, at the investigator discretion, Grade ≤2 if not considered a safety risk for the patient).

If a treatment delay results from worsening of hematologic or biochemical parameters, the frequency of relevant blood tests should be increased as clinically indicated. Patients experiencing Grade 3 or 4 potentially treatment related toxicity or intolerable Grade 2 toxicity despite supportive care should have their treatment interrupted/delayed. Appropriate follow-up assessments should be done until adequate recovery (or until deemed irreversible) occurs as assessed by the Investigator.

If these conditions are met within 2 weeks of treatment interruption or cycle delay, PF-04518600 or PF-04518600/utomilumab may be resumed. For monotherapy, please refer to Section 5.4.5.6.1 (Dose Reductions, Interruptions and Discontinuation Part A Monotherapy) for adverse events requiring dose reduction at the time of treatment resumption. For combination therapy, intrapatient dose reduction will not be permitted (see Section 5.4.5.6.2 Dose Reductions, Interruptions and Discontinuation Part B Combination Therapy).

If these conditions are not met, treatment resumption must be delayed up to a maximum of 4 weeks. If these parameters have not been met after 4 weeks of dose interruption or 4 weeks of new cycle delay, permanent discontinuation of treatment with PF-04518600 or PF-04518600/utomilumab should be considered. Treatment resumption for patients

recovering from treatment-related toxicity after 4 weeks of treatment interruption or cycle delay can be considered only if the patient is deemed to be deriving obvious clinical benefit per the investigator's best medical judgment and needs to be agreed between the investigator and the sponsor.

If a treatment interruption continues beyond Day 14 of the current cycle, then the day when treatment is restarted will be counted as Day 1 of the next cycle.

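### Table 5 (Part A): the Grade 4 neutropenia trigger gives ANC <500/mm³ as 1.0 x 10⁹/L; the correct figure is 0.5 x 10⁹/L

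*Protocol*

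**What the plan says.** Protocol Section 5.4.5.6.1 introduces the table with "Recommended dose reductions are illustrated in Table 5". In the drug-related hematologic toxicity row, the first trigger reads "Grade 4 neutropenia, ie, ANC <500 mm³ (1.0 x 10" to the ninth per litre), for more than 7 days. The next trigger in the row is "Febrile neutropenia, ie, fever >38.3°C or a sustained temperature", with ANC below 1,000/mm³. The action is to hold until the counts recover and then "Reduce PF-04518600 by 1 dose level". The ANC recovery threshold is given as 1.0 x 10⁹/L, with its equivalent printed as "1,000 cells/mm³) and platelets" (the platelet threshold follows). The same section adds: "Dose re-escalation is not allowed".

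Three other places bear on the point:

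- Section 4.1.1, criterion 6, under "ANC for HCC only", sets the entry limit at 1,000/mm³ and gives 1.0 x 10⁹/L as its equivalent.
- Section 3.2 lists Grade 4 neutropenia of more than 7 days as a DLT and gives no count.
- Section 5.4.5.5 says that re-treatment after an interruption for toxicity or "at the start of any new cycle may not occur until all of the following parameters have been met"; the ANC parameter there is at least 1,000/mm³.

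**The concern.** The two units in one trigger disagree by a factor of two. Someone reading the count per mm³ would act below 500; someone reading the SI figure would act below 1,000. The protocol prints many of its count thresholds in both units and the study is multi-center, with sites in France and the Netherlands among others (Document History, Amendment 5), so it is reasonable to expect some sites to work from the SI figure.

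Read in SI units, the line would recommend a one-level reduction for a patient without fever whose drug-related ANC stays between 500 and 999/mm³ for more than 7 days. That is not Grade 4 by the line's own count, and it goes beyond the matching DLT criterion. Because re-escalation is barred, a reduction made on that reading would stay with the patient. For HCC patients, the only population now planned for Part A2, the misprinted figure also equals the ANC entry limit.

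**Working it through.** **Conversion.** 1 L = 10⁶ mm³, so the value in 10⁹/L is (cells/mm³ x 10⁶) / 10⁹.

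**Every paired count in the Table 5 row, with the paired entry limits from Section 4.1.1:**

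| Threshold | Per mm³ | Printed (10⁹/L) | Computed (10⁹/L) | Agrees |
|---|---|---|---|---|
| Table 5, ANC trigger | 500 | 1.0 | 0.5 | **No** |
| Table 5, ANC recovery | 1,000 | 1.0 | 1.0 | Yes |
| Table 5, platelets, Grade 4 | 25,000 | 25.0 | 25.0 | Yes |
| Table 5, platelets, Grade 3 | 50,000 | 50.0 | 50.0 | Yes |
| Table 5, platelet recovery | 75,000 | 75 | 75 | Yes |
| Entry, ANC, non-HCC | 1,500 | 1.5 | 1.5 | Yes |
| Entry, ANC, HCC | 1,000 | 1.0 | 1.0 | Yes |
| Entry, platelets, non-HCC | 100,000 | 100 | 100 | Yes |

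The printed SI figure cannot be reproduced from 500/mm³. In reverse, 1.0 x 10⁹/L divided by 10⁶ mm³/L is 1,000/mm³, and 1,000 / 500 = 2.

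**Which of the two figures is wrong.** The Grade 4 label, the leading <500 count and the Grade 4 DLT criterion in Section 3.2 agree with each other. Read as <1.0 x 10⁹/L, the trigger would sit exactly at the recovery threshold in its own action cell, at the ANC cut-off of the febrile neutropenia bullet (making the fever requirement redundant once the count had been low for more than 7 days), and at the re-treatment threshold of Section 5.4.5.5. The SI figure is therefore the error.

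**Who falls between the two readings.** Patients with a drug-related ANC of 500-999/mm³ for more than 7 days who are not febrile. Febrile patients below 1,000/mm³ already get the same action from the next bullet.

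**Fall from the entry limit needed to go below the trigger**, as (limit - trigger) / limit:

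- HCC, limit 1,000/mm³. SI figure as printed: (1,000 - 1,000) / 1,000 = 0%, so any fall. Corrected: (1,000 - 500) / 1,000 = 50%, so more than half.
- Non-HCC, limit 1,500/mm³. SI figure as printed: (1,500 - 1,000) / 1,500 = 33%. Corrected: (1,500 - 500) / 1,500 = 67%.

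These are distances on the ANC scale only. The trigger also needs attribution to the drug and persistence for more than 7 days, so they are not estimates of how often it would be met.

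**Frequency.** The Amendment 6 rationale in the Document History reports 1 of 52 Part A1 patients with a treatment-related Grade 2 neutrophil decrease: 1 / 52 = 1.9%. No rate is given for the 500-999/mm³ band, so no patient count is estimated.

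**The case against.** The conversion itself is not open to dispute; the objection is that it hardly matters.

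- **The text above the table already excludes the misuse.** Section 5.4.5.6.1 plans no reductions for toxicities outside the DLT list, apart from recurrent, intolerable Grade 2 events. An afebrile ANC of 500-999/mm³ without infection is not on that list, and Section 3.2 lets other toxicities be considered DLTs only after review by the sponsor and investigators. This is a good argument that 0.5 is the intended value. It does not remove the contradictory number from the table that sites will consult, and Section 5.4.5.5 sends investigators to this section for events that require a reduction.
- **A reader has enough cues.** The Grade 4 label, the <500 count and the correctly converted recovery threshold alongside all point the right way. This stands, and is the main reason the point is minor.
- **The table only recommends.** Reductions are recommended, investigators keep their judgment, and the row requires attribution to the drug. This also stands.
- **The HCC entry limit adds little.** A patient entering at 1,000/mm³ already has no margin for starting a new cycle under Section 5.4.5.5, misprint or not. That is right as regards holds. The misprint adds the recommended dose reduction to the delay. The conclusion does not rest on this point.
- **Exposure is small.** Part B does not use intrapatient reduction for individual toxicity, and 52 of about 58 planned Part A1 patients had been treated by 24 May 2017, before Amendment 6. This stands.

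**Conclusion.** The SI figure in the Table 5 Grade 4 neutropenia trigger is wrong by a factor of two: it should be 0.5, not 1.0 x 10⁹/L. This follows from unit conversion and from the protocol's own pairings, and needs no outside assumption. That <500/mm³ is the intended threshold is inferred from the grade label, the DLT criterion and the rest of the row.

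The consequence is minor. It is limited to dose reduction in afebrile Part A patients in the 500-999/mm³ band, and the error is toward less drug. Holds are largely unaffected, because a new cycle is already barred below 1,000/mm³. No DLT count, MTD rule, sample size or analysis uses the figure. What remains is that a site reading SI units could make a lasting reduction that the line does not intend. The correction should be made because the number sits in a dose-modification threshold.

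**What to change.** In Table 5, Grade 4 neutropenia trigger, change the parenthetical 1.0 x 10⁹/L to 0.5 x 10⁹/L. No other threshold in the row needs to change, and the SAP is unaffected. The cost is a one-figure correction, made at the next amendment or by an administrative change letter, a route the sponsor has already used in this study.

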# 5.4.5.6.2. Part B Combination Therapy

Intrapatient dose reductions are not permitted during the combination therapy with PF-04518600 and utomilumab unless, in discussion with the sponsor, a dose combination level is deemed to be above the determined MTD for the combination.

Given the expected similarities of side effect profile and mechanism between the two co-stimulation monoclonal antibodies, both treatments must be interrupted or discontinued together. Patients will not be permitted to continue treatment with one agent, while the other agent is either interrupted or permanently discontinued. If infusion related reactions are observed following the administration of the first agent, administration of the second agent will be withheld until symptoms resolve (see Section 5.4.5.1 Infusion Reactions).

Treatment of irAEs should follow guidelines set forth in Table 4 in Section 5.4.5.4 Recommended dose modifications for any other drug-related toxicity are illustrated in Table 6.

Table 6. Treatment Interruptions/ Discontinuations for Drug Related Toxicity at Start of Subsequent Cycle

Toxicity	NCI CTCAE Severity Grade	Treatment Modifications
Hematologic abnormalities.	Grade 3	
 
Withhold until recovery to Grade 1 or better.
 
If toxicity does not resolve to Grade 1 or better within 4 weeks of last infusion, consider permanent discontinuation after consultation with the sponsor.
 
Upon the second occurrence of the same Grade 3 toxicity that does not resolve to Grade ≤1 by the next administration, treatment must be permanently discontinued.
 

	Grade 4	Permanent discontinuation.     Exceptions are:     Single laboratory values out of normal range that are unlikely related to investigational product (s) as assessed by the Investigator, do not have any clinical correlate, and resolve within 7 days with adequate medical management.
Infusion-related reaction.	Grade 1-4	• See Section 5.4.5.1 and Appendix 4.
Hypersensitivity reaction.	Grade 1-4	• See Section 5.4.5.2 and Appendix 4.
Other non-hematologic toxicities and laboratory abnormalities.	Grade 2	
 
If toxicity resolves to Grade ≤1 by the next administration, treatment may continue.
 
If toxicity does not resolve to Grade ≤1 by the next administration despite optimal treatment, the next infusion should be omitted. If at the end of 4 weeks of dose holding, the event has not resolved to Grade ≤1, the patient should permanently discontinue treatment (except for hormone deficiencies that can be managed by replacement therapy and for which up to 2 additional subsequent doses may be omitted).
 

Table 6. Treatment Interruptions/ Discontinuations for Drug Related Toxicity at Start of Subsequent Cycle

Toxicity	NCI CTCAE Severity Grade	Treatment Modifications
	Grade 3	Permanent discontinuation, Exceptions are:
		
 
Transient (≤6 hours) flu-like symptoms or fever, which is controlled with medical management.
 
Transient (≤24 hours) fatigue, local reactions, headache that resolves to Grade ≤1.
 
Nausea and vomiting controlled by medical therapy.
 
Diarrhea, skin toxicity, or liver function test (ALT, AST, or Gamma-glutamyltransferase [GGT]) that resolves to ≤ Grade 1 in less than 7 days after medical management (eg, immunosuppressant treatment) has been initiated.
 
Amylase or lipase abnormality that is not associated with symptoms or clinical manifestations of pancreatitis.
 
Tumor flares phenomenon defined as local pain, irritation, or rash localized at sites of known or suspected tumor.
 
Non hematologic laboratory abnormality that do not require medical intervention or hospitalization.
 
Single non hematologic laboratory values out of normal range that are unlikely related to treatment as assessed by the Investigator, do not have any clinical correlate, and resolve to ≤ Grade 1 within 7 days with adequate medical management.
 

	Grade 4	Permanent discontinuation, Exceptions are:
		
 
Non hematologic laboratory abnormality that does not require medical intervention or hospitalization. Single non hematologic laboratory values out of normal range that are unlikely related to treatment as assessed by the Investigator, do not have any clinical correlate, and resolve within 7 days with adequate medical management.
 
Amylase or lipase abnormality that is not associated with symptoms or clinical manifestations of pancreatitis.
 

# 5.4.6. Treatment after Initial Evidence of Radiological Disease Progression

Immunotherapeutic agents such as PF-04518600 and/or utomilumab may produce antitumor effects by potentiating endogenous cancer-specific immune responses. The response patterns seen with such an approach may extend beyond the typical time course of responses seen with cytotoxic agents, and can manifest as a clinical response after an initial increase in tumor burden or even the appearance of new lesions.

If radiologic imaging shows disease progression, tumor assessment should be repeated ≥4 weeks later in order to confirm the progression (See Appendix 6). Assigned study treatments may be continued at the Investigator's discretion while awaiting radiologic confirmation of disease progression.

Patients may receive study treatments while waiting for confirmation of progressive disease (PD) if they are clinically stable as defined by the following criteria:

- Absence of clinical signs and symptoms (including worsening of laboratory values) of disease progression.
- No decline in ECOG performance status.
- Absence of rapid progression of disease by radiographic imaging.
- Absence of progressive tumor at critical anatomical sites (eg, cord compression) requiring urgent alternative medical intervention.

If repeat imaging no longer shows PD but rather CR, PR or SD compared to the initial scan, treatment may be continued/resumed. In determining whether or not the tumor burden has increased or decreased, Investigators should consider all target as well as non-target lesions (refer to the Appendix 6).

If the repeat imaging confirms PD, patients should be considered for discontinuation from both investigational products. However, according to the Investigator's clinical judgment and after discussion between the Investigator and the Sponsor, if a patient with evidence of PD is still experiencing clinical benefit, the patient may be eligible for continued treatment with both investigational products. The Investigator's judgment should be based on the overall benefit-risk assessment and the patient's clinical condition, including performance status, clinical symptoms, adverse events and laboratory data.

Patients who stop treatment for reasons other than toxicity with either or both investigational products and then experience radiologic disease progression shortly thereafter will be eligible for re-treatment with either or both investigational products at the discretion of the Investigator and after discussion with the Sponsor.

